Metastatic Dissemination (MD): Refers to the appearance after protocol therapy of cancer deposits characteristic of metastatic dissemination from NSCLC. Appropriate evaluations for making this determination include physical examination and imaging studies. PET scan OR biopsy to confirm MD is encouraged but not required.

PFS at the primary site: Patient remains alive without **local** progression (**LP**) at the primary site.

Criteria for going off proton treatment:

1. Development of distant metastasis during the proton radiotherapy.
2. Development of unpredictable, irreversible, or persistent non-hematological grade 4 toxicity.
3. Patient refusal or non-compliance of treatment requirements.

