9.0 Statistics

The local control rate at 2 years is 50% with historical photon data. We anticipate that proton therapy will increase the local control rate to 75%. With a sample of 40 patients we will have 93% power to detect an increase in the local control rate at 2 years from 50% to 75% with a 1-sided significance level of 5%. This calculation assumes that we will accrue 20 patients per year for 2 years and that we will follow all patients for 2 years. We will estimate the local control rate at 2 years with a 95% confidence interval using the Kaplan-Meier product-limit estimator.

With current photon therapy using similar relative biological effectiveness (RBE) the rate of grade 3 acute pneumonitis is less than 15%, and the chronic pneumonitis rate is 15%. With a sample of 40 patients we will have 81% power to detect a decrease in the rate of grade 3 acute pneumonitis from 15% to 3.75% with a 1-sided significance level of 5%. We will estimate the

grade 4 acute pneumonitis rate with an exact binomial 95% confidence interval.

We will enroll and evaluate a maximum of 40 patients at a rate of 20 patients per year. We will monitor the rate of grade 3+ pneumonitis, which is assessed within 3 months following completion of therapy. Our target grade 3+ pneumonitis rate is 10% or less, based on RTOG Study 9311. We assume a beta(0.2, 1.8) prior distribution for this toxicity rate. This prior distribution has a mean of 10% and a standard deviation of 17%.

We will stop the trial early if $P(\text{grade 3+ pneumonitis} > 10\% \mid \text{data from the trial}) > 0.925$. That is, given the outcomes from the patients who have already been evaluated, if we determine that there is more than a 92.5% chance that the grade 3+ pneumonitis rate is more than 10% we will stop the trial. This decision rule gives the following stopping rule. Stop the trial if

$$\begin{aligned}
 & [\# \text{ of pts with grade 3+ pneumonitis} / \# \text{ of pts evaluated}] \\
 & \geq 4/15, 5/17, 6/24, 7/31, 8/38
 \end{aligned}$$

The operating characteristics of this monitoring rule are shown in Table 1.

Grade 3+ Pneumonitis Rate	Probability of Stopping Early	Sample Size		
		P ₂₅	P ₅₀	P ₇₅
0.050	0.012	40	40	40
0.075	0.053	40	40	40
0.100	0.131	40	40	40
0.150	0.413	21	40	40
0.200	0.709	15	22	40
0.250	0.895	15	15	25
0.300	0.970	15	15	16

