Once we have completed the study we will estimate the grade 3+ pneumonitis rate with a 90% credible interval. If we have grade 3+ pneumonitis in 4 of the 40 patients (10%), then our 90% credible interval for the grade 3+ pneumonitis rate will be 3.7% to 18.5%. If we have grade 3+ pneumonitis in 2 of the 40 patients (5%), then our 90% credible interval for the grade 3+ pneumonitis rate will be 1.1% to 11.8%.

In addition, if there is any grade 4 or 5 toxicity directly caused by proton therapy, the trial will be re-evaluated and decision will be made about modification of treatment or stopping the trial.

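### Power is stated for grade 3 acute pneumonitis against 15%, but the exact interval that follows is for grade 4, and no sentence names the analysis that makes the comparison with 15%

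*Combined protocol and SAP*

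**What the plan says.** Section 1.0 makes reduced acute and chronic toxicity a primary goal. Section 9.0 carries this into one powered hypothesis.

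- **Benchmark:** with photons, "the rate of grade 3 acute pneumonitis is less than 15" percent.
- **Power:** 40 patients give "81% power to detect a decrease in the rate of grade 3 acute pneumonitis from 15% to 3.75" percent, at a one-sided 5% level.
- **Interval, in the next sentence:** the plan will estimate the "grade 4 acute pneumonitis rate with an exact binomial 95% confidence interval".
- **Monitoring:** "We will monitor the rate of grade 3+ pneumonitis, which is assessed within 3 months following completion of therapy". The reference rate here is 10%, not 15%.
- **End of study:** "we will estimate the grade 3+ pneumonitis rate with a 90% credible interval". It is illustrated at 4/40 and 2/40, with no mention of 15% and no decision rule.

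Section 2.0 says that toxicities will be compared with historical photon data. Section 5.2 says that grade 3 or higher toxicities will be analysed. Neither gives a method.

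**The concern.** In the local control paragraph of Section 9.0, one quantity is powered and the same quantity is then estimated. In the pneumonitis paragraph the endpoint changes between the two sentences. Grade 4 pneumonitis has no hypothesis, benchmark or power statement. Followed literally, the exact analysis placed beside the only powered toxicity hypothesis is run on another endpoint, and it cannot show whether the grade 3 rate is below 15%.

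The grade label also varies. The power sentence says grade 3, while the monitoring and end-of-study text say grade 3+. Section 2.0 quotes the historical rate for grade 3 or higher. These are not the same count if a grade 4 or 5 case occurs.

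At stake is whether the result on a primary toxicity goal is read from an analysis fixed in advance.

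**Working it through.** **Inputs (Section 9.0).** n = 40, null rate 15%, alternative 3.75%, one-sided alpha 5%, prior beta(0.2, 1.8). X is the number of patients with the event.

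**Step 1. Reproduce the 81%.** Exact binomial test, rejecting at X ≤ 2, with P(X = k) = C(40, k) p^k (1 − p)^(40 − k):

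| k | p = 0.15 | p = 0.0375 |
|---|---|---|
| 0 | 0.85^40 = 0.0015 | 0.9625^40 = 0.2168 |
| 1 | 40 × 0.15 × 0.85^39 = 0.0106 | 40 × 0.0375 × 0.9625^39 = 0.3378 |
| 2 | 780 × 0.15² × 0.85^38 = 0.0365 | 780 × 0.0375² × 0.9625^38 = 0.2567 |
| Sum | **0.0486** | **0.8113** |

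Rejecting at 3 or fewer would give alpha 0.1302, so 2 is the largest valid cut-off. The stated 81% is therefore correct for the exact test. A one-sided normal approximation gives 74.3% and an arcsine approximation 82.1%, so the exact test is the natural reading of the power sentence.

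**Step 2. Does monitoring disturb this?** The listed stopping boundaries (4/15, 5/17, 6/24, 7/31, 8/38) all need at least 4 events. They cannot stop a trial that would end with 2 or fewer, so the alpha and power in step 1 stand. The re-evaluation clause for grade 4 or 5 toxicity has no numerical rule and is not in these figures.

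**Step 3. Change only the grade in the interval sentence.** The Clopper-Pearson limits at 2/40 are the α/2 quantile of beta(2, 39) and the 1 − α/2 quantile of beta(3, 38):

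- Two-sided 95%: 0.61% to 16.92%, which includes 15%.
- Two-sided 90% (its upper limit is the one-sided 95% bound): 0.90% to 14.92%, which excludes 15%.

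At 2 events the powered test rejects 15%, but the 95% interval printed beside it would still contain 15%. The 90% interval agrees with the test.

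**Step 4. Does the credible interval already answer the question?** The posterior is beta(0.2 + x, 1.8 + 40 − x), with 5% in each tail:

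- 2/40: 1.08% to 11.79% (the plan gives 1.1% to 11.8%).
- 4/40: 3.70% to 18.47% (the plan gives 3.7% to 18.5%).
- 3/40: upper limit 15.24%.

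Both published intervals reproduce. If the interval were read against 15%, it would give the same cut-off of 2 at n = 40. The plan does not say to read it that way.

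**The case against.** The strongest reply is that this is a slip in one digit. The power sentence already fixes the endpoint, null, alternative, n, sidedness and alpha, and only the exact test among those tried gives 81%, so the test and its cut-off of 2 can be recovered. Section 2.0 states the intent to compare. In the local control paragraph a one-sided 5% power statement is likewise followed by a 95% interval for estimation, so the pneumonitis interval may never have been meant as a decision tool. Grade 4 toxicity also has uses of its own: "persistent non-hematological grade 4 toxicity" is an off-treatment criterion, and "if there is any grade 4 or 5 toxicity directly caused by proton therapy, the trial will be re-evaluated".

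Much of this stands. A descriptive grade 4 interval is legitimate, and the test is recoverable. But the text does not settle whether grade 4 is a slip, and no sentence names the test or ties any estimate to 15%.

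A reader might infer more than the documents support:

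- **That the powered comparison cannot be carried out, or that the 81% is wrong.** Step 1 shows otherwise.
- **That the real power is 55.5%.** That is P(X ≤ 1 | 0.0375) at n = 40, and it applies only if the two-sided 95% interval is the decision rule. The plan never adopts that rule.
- **That the exact test and the credible interval conflict.** At 40 they give the same cut-off. At 2/39 they would part (p = 0.0547 against a credible upper limit of 12.1%), but only if the credible interval were used as a test, which the plan does not do. Section 9.0 says "We will enroll and evaluate a maximum of 40 patients", and the documents give no expected shortfall.

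The choice of 15% when the historical rate is only described as below 15% is a separate benchmark question and is not part of this point.

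**Conclusion.** The point holds as a mismatch between the powered endpoint and the stated analysis. Power is for grade 3 acute pneumonitis against 15% and is correctly computed. The exact interval beside it is for grade 4, and the grade 3+ credible interval carries no reference to 15%. Replacing 4 with 3 does not finish the repair: at 2/40, the largest count at which the test rejects, a two-sided 95% interval reaches 16.9% while the one-sided 95% bound is 14.9%.

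These figures assume 40 evaluable patients and the exact binomial test implied by the stated power. The correction should be made because reduced toxicity is a primary goal and this is its only powered hypothesis. It does not call into question the sample size, the 81% or the pneumonitis monitoring rule.

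**What to change.** In Section 9.0:

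1. Write grade 3 or higher acute pneumonitis in the historical-rate, power and interval sentences, to match Section 5.2 and the monitoring text.
2. State that the comparison with 15% is the exact one-sided 5% binomial test, rejecting at 2 or fewer events in 40. If the evaluable number differs, recompute the cut-off from the same test.
3. Report the exact one-sided 95% upper bound with it (equivalently the two-sided 90% interval, 0.9% to 14.9% at 2/40).
4. Say that the 90% credible interval is the supporting estimate.
5. If a grade 4 interval or a two-sided 95% interval is kept, label it descriptive.

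**Cost.** A few sentences. Sample size, monitoring and the 81% power with 40 evaluable patients are unchanged. A one-sided 95% bound replaces the conventional 95% interval for this endpoint. Holding 5% strictly also has a price if patients are lost: at 39 evaluable, P(X ≤ 2 | 0.15) = 0.0547, so the cut-off drops to 1 and power to 56.8%. That follows from the discreteness of the exact test, and stating the rule makes it visible in advance.

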5.0 Evaluation Criteria

5.1 Treatment evaluation:

Acute radiation reactions including esophagitis, pneumonitis and other adverse events will be evaluated weekly during the course of treatment. The adverse events will be graded according to the National Cancer Institute (NCI) Common Terminology Criteria for Adverse Events, version 3.0 (CTCAE 3.0). Laboratory studies will include a CBC with differential, platelet count every three weeks during the radiotherapy.

5.2 Post-treatment evaluation:

Patient follow-up is recommended 6 weeks after RT and then required every 3 months (± 1 month) for two years, then every 6 months (± 1 month) for three years and then annually for the rest of the patient's life, which is the standard of care. For the purpose of this protocol, we are going to follow the patients for a minimum of two years. Afterwards, patients will be continuously followed according to the standard of care. Follow-up will be conducted at the treating institution or other clinical facilities. If the follow-up is performed at other facilities, the information about medical history, physical examination, PFT, image data and radiologist's report must to be sent to the treating institution to be reviewed and documented. Follow-up at the treating institution is strongly recommended.

Two Pulmonary function tests will be performed within first one year ± 5 month after the completion of RT, then annually for two years. It is preferred that PFT is performed in the second and fourth follow up visit after completion of concurrent radiotherapy and chemotherapy, and then annually for two years. If no 6 week follow-up, then PFT is preferred to be performed in the first and third visit. EKG will be conducted in the third or fourth f/u visit and then annually for two years. If cardiac toxicity is of concern based on treatment plan and/or when EKG is abnormal, cardiac SPECT should be performed in the third or fourth f/u visit and then as clinically indicated. Physical examination, medical history, and CXR will be performed in every follow up. A chest CT scan will be performed in the second follow up after radiotherapy and then every three months (± 1 month) for two years and then every 6 months (± 1 month) for 3 years; then annually. PET scan is required between 2-6 months after finishing treatment, including chemotherapy, When a PET scan is available for the follow up visit, a chest CT is not required for this visit. A PET/CT scan is preferred whenever possible.

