- Obtain chest CT if symptoms. If no symptoms, obtain chest CT in the second follow up after completion of radiotherapy and then every 3 months (+/-1 month) during years 1 and 2, then every 6 months (+/- 1 month) for three years and then annually. Brain scan is indicated if patient develops neurological symptoms. PET scan is required between 2-6 months after finishing treatment including chemotherapy if it is given. When PET is available, chest CT is not required. PET scan is required to evaluate recurrent disease.

- h. 10 ml of additional peripheral blood will be collected at the time of pre-registration blood work up. The blood sample will be frozen using a -80 degree centigrade refrigerator for future biomarker study.
- i. Radiotherapy need not start on a Monday but shall not start on a Friday.
- j. 4D-CT scanning will be performed at least in weeks 3 or 4 and 7
- k. 4DCTs in weeks 1, 2,5,and 6 are optional.

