7.2 Radiation Doses

7.2.1 The total radiation dose for the tumor target will be 87.5 Cobalt Gray Equivalent (CGE) at 2.5 CGE per fraction, once a day, 5 fractions per week. 100% of the iCTV should be covered by the prescribed dose. For proton treatments this will be achieved by ensuring that each beam covers the iCTV plus the margins for not only lateral but also range uncertainties (ICRU 78). Caution should be used as beams should not be modified based on a static evaluation.

7.2.2 Normalization of the treatment plan will cover 95% of the PTV with the prescription dose. The minimum PTV dose must not fall below 95% of the prescription dose. The PTV is assumed to be the beam-specific PTV.

7.2.3 Deviations from dose prescription for target volumes:

7.2.3.1 No deviation: $\geq 99\%$ of the PTV receives $\geq 95\%$ of the prescribed dose, and a contiguous volume of no more than 2 cc inside PTV exceeds 110% of the prescribed dose.

7.2.3.2 Minor deviation: Deviations of this magnitude are not desirable, but are acceptable. Coverage that is equal to 95% of the prescribed dose and falls between 99% and 95% of the PTV, or a contiguous volume of no more than 2 cc inside the PTV exceeds 120% of the prescribed dose. Similar considerations apply for each beam-specific PTV.

7.2.3.2 Major deviation: Coverage that is less than 95% of the prescribed dose and falls between 99% and 95% of the PTV, or a contiguous volume of greater than 2 cc inside the PTV exceeds 120% of the prescribed dose. Similar considerations apply for each beam-specific PTV.

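### Does the stopping-rule table understate how many patients would be enrolled when the pneumonitis rule stops the trial?

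*Combined protocol and SAP*

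**What the plan says.** The monitoring text is in Section 9.0 Statistics. The endpoint is timed thus: "We will monitor the rate of grade 3+ pneumonitis, which is assessed within 3 months following completion of therapy". The posterior is computed "given the outcomes from the patients who have already been evaluated", and the printed boundaries (4/15, 5/17, 6/24, 7/31, 8/38) have patients evaluated as their denominator. The plan then says "The operating characteristics of this monitoring rule are shown in Table 1". The relevant column of that table is headed only as sample size, with quartiles of 15/22/40, 15/15/25 and 15/15/16 at true rates of 20%, 25% and 30%.

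On accrual, the same section says "We will enroll and evaluate a maximum of 40 patients at a rate of 20 patients per year", and of the local-control power figure, "This calculation assumes that we will accrue 20 patients per year for 2 years". Section 7.2 gives 87.5 CGE at "2.5 CGE per fraction, once a day, 5 fractions per week". Section 5.1 adds that acute reactions including pneumonitis "will be evaluated weekly during the course of treatment". No section says whether accrual pauses while outcomes are pending, and none gives the number enrolled at stopping.

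**The concern.** Someone judging patient protection will read a median of 15 at a 25% or 30% pneumonitis rate as the number of patients exposed before the trial stops. The plan's own timing does not support that reading. A patient takes about seven weeks to treat and may not be fully assessed until three months later, while another patient enrols roughly every 2.6 weeks (52/20). Unless accrual is held, several more patients will have entered by the time the 15th is evaluated.

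If the column were meant as enrolment, the plan's only statement of exposure under an unsafe regimen would be too low by about a third to two thirds at those rates. Some crossings would also come after the 40th patient had enrolled, so they would not count as early stopping in the enrolment sense.

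**Working it through.** **Inputs.** Prior beta(0.2, 1.8), cut-off 0.925, first boundary at 15 evaluated, maximum 40, accrual 20 per year, assessment up to 3 months after therapy (Section 9.0). Total dose 87.5 CGE in 2.5 CGE fractions, 5 per week (Section 7.2).

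**1. Boundaries.** With x events in n evaluated, the posterior is beta(0.2 + x, 1.8 + n − x). For 4 of 15 it is beta(4.2, 12.8), with P(rate > 10%) = 0.947, so stop. For 4 of 16 the probability is 0.935, so stop. For 4 of 17 it is 0.922, so continue; 5 of 17 gives 0.979. The minimum counts are 4 at n = 15–16, 5 at 17–23, 6 at 24–30, 7 at 31–37 and 8 from 38, as printed.

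**2. The plan's table.** Exact binomial recursion, one evaluated patient at a time, looks at n = 15 to 39:

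| True rate | P(stop), table | P(stop), recomputed | Quartiles, table | Quartiles, recomputed |
|---|---|---|---|---|
| 10% | 0.131 | 0.134 | 40/40/40 | 40/40/40 |
| 15% | 0.413 | 0.417 | 21/40/40 | 21/40/40 |
| 20% | 0.709 | 0.711 | 15/22/40 | 15/22/40 |
| 25% | 0.895 | 0.893 | 15/15/25 | 15/15/25 |
| 30% | 0.970 | 0.970 | 15/15/16 | 15/15/16 |

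The probabilities agree to within 0.5 percentage points and every quartile matches. The column counts patients evaluated.

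**3. Does the delay spoil the table?** No. If outcomes are counted in order of enrolment, the n at which the boundary is crossed depends only on the sequence of outcomes, not on the calendar. A lag moves the date of the crossing, not the evaluated count. The table therefore needs no assumption of immediate outcomes. That assumption, or a hold, is needed only to read the column as patients enrolled.

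**4. Patients enrolled at stopping.** Treatment takes 87.5/2.5 = 35 fractions, and 35/5 = 7 weeks. If treatment starts at enrolment and outcomes count when the window closes, the lag is 7/52 + 0.25 = 0.385 years, and 20 × 0.385 = 7.7 further patients enrol. With evenly spaced accrual that is 7 whole patients, so enrolled = min(40, evaluated + 7), for example 15 + 7 = 22. Enrolled quartiles are then 22/29/40, 22/22/32 and 22/22/23 at 20%, 25% and 30%. At 15% they are 28/40/40, so the median does not move.

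Median enrolled under other timings, all without a hold (even accrual; Poisson accrual):

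| Time from enrolment to known outcome | Patients entering in the lag | 20% | 25% | 30% |
|---|---|---|---|---|
| 7 weeks + 6 weeks | 5.0 | 27; 27 | 20; 22 | 20; 21 |
| 7 weeks + 3 months | 7.7 | 29; 30 | 22; 25 | 22; 24 |
| 8 weeks + 3 months | 8.1 | 30; 31 | 23; 25 | 23; 24 |
| 1 month to start + 7 weeks + 3 months | 9.3 | 31; 32 | 24; 27 | 24; 25 |

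The 8-week row reflects the schema, which shows radiotherapy in weeks 1 to 8 and says "Radiotherapy need not start on a Monday but shall not start on a Friday".

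**5. Stopping before enrolment is complete.** With a 7-patient lag the crossing must come at 40 − 1 − 7 = 32 evaluated or fewer. The probability is 0.642, 0.840 and 0.943 at 20%, 25% and 30%, against 0.709, 0.895 and 0.970 in the table for the rule being triggered at all.

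**6. What a hold would cost.** Patient 15 enrols at 14/20 = 0.70 years and is evaluable at about 1.08. Holding patient 16 from 0.75 to 1.08 adds about 0.33 years (4 months) and moves patient 40 from 39/20 = 1.95 to 2.28 years.

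**The case for a change.** The strongest case for a change is that the table is the only place where the plan shows how many patients are exposed before an unsafe regimen is stopped. Its header does not say evaluated, and the same section uses the word sample for the 40 to be enrolled. Every timing tried without a hold gives a median above 15 at 25–30%. The rates of 20% and above are also the ones the rule exists to catch, so it is no full answer that they are unlikely.

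Much of this stands. The direction is right, the arithmetic is right, and the header could be clearer. Three parts do not carry through.

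- The table does not rest on an unrealistic no-delay assumption (step 3).
- The plan's silence on a hold is not evidence that none would be used. The accrual rate is a planning assumption, and a four-month pause at the first boundary is feasible.
- The excess is limited to high true rates. Section 2.0 lists no grade 3 pneumonitis among 15 earlier patients at the same dose. If there was none, the probability of that is 0.85^15 = 8.7% at a true rate of 15%, 0.80^15 = 3.5% at 20%, 0.75^15 = 1.3% at 25% and 0.70^15 = 0.5% at 30%.

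Weekly grading during treatment, and the re-evaluation in Section 9.0 after any grade 4 or 5 toxicity caused by proton therapy, give some further protection. The latter does not cover grade 3 events.

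**Conclusion.** No change is needed. The printed quartiles are correct for patients evaluated, which is the count on which the rule is written and which the table is introduced as describing. A reader who wants the number enrolled can get it from the plan's own accrual rate and assessment window: about 20 to 25 at a 25–30% rate, against 15 evaluated, and about 27 to 31 at 20%, against 22. These ranges assume treatment starts at enrolment, accrual continues at 20 per year, and outcomes are known between 6 weeks and 3 months after a 7- or 8-week course. A further month before treatment starts would raise the upper ends to 27 and 32. At 15% or below the median is 40 on either count.

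What is missing is a word in a column header and a statement of what happens to accrual while outcomes are pending, and those running the trial can settle both sensibly. Adding enrolled-patient columns would describe the rule more fully, but it would leave the boundaries, the 0.925 cut-off, the probability of triggering and the 40-patient maximum untouched. Following the plan as written still gives a sound stopping decision.

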2. Bush reported his experience in 27 patients with stage I NSCLC treated with proton and photon radiotherapy. The total dose was 73.8 Gy with 45 Gy delivered with photons (1.8 Gy/fraction) and 28.8 CGE delivered with protons (1.8 CGE/fraction). Proton treatments and the last 16 fractions of photon treatments were given as BID. The local control was 87% and the 2-year disease free survival was 86%. Only two patients developed pneumonitis which resolved after oral steroid treatment.
3. Japan National Cancer Center Hospital East reported their result of 36 patients with stage I NSCLC treated with proton radiotherapy to a total dose of 70-94 CGE delivered in 20 fractions. The 2-year local control was 92.6% and the overall survival was 81%. No grade 2 or above acute toxicities were observed. Late grade 3 toxicities were observed in 3 patients. Among 19 patients with stage IB disease, two had local progression and eight developed regional lymph node and/or distant metastasis. Again, understaging without PET could be a concern here.

4. MD Anderson Cancer Center analyzed our preliminary data of phase I/II study in early stage NSCLC treated with dose escalated/accelerated proton therapy (IASLC 2009 presentation). Fifteen patients with medical inoperable T1N0M0 (central location) or T2-3N0M0 (any location) NSCLC were treated on our phase I/II study using dose-escalated proton therapy to 87.5 cobalt-Gray equivalents (CGE) at 2.5 CGE/fraction without adjuvant chemotherapy. At a median follow-up time of 16.5 months (range, 5-24.1 months), no patient had experienced grade 4 or 5 toxicity. The most common adverse effect was dermatitis (grade 2, 11 patients [73%], grade 3, 2 patients [13%]), followed by grade 2 fatigue (5 patients [33%]), grade 2 pneumonitis (1 patient [7%]), grade 2 esophagitis (1 patient), and grade 2 chest wall pain (1 patient). Rates of local control were 93% (14/15), regional lymph node failure 7% (1/15), and distant metastasis 20% (3/15). Twelve patients (80%) were still alive at last follow-up; 2 had died of metastatic disease and 1 of preexisting cardiac disease. In conclusion, proton therapy escalated to ablative doses is well tolerated and produces promising local control rates for medically inoperable early-stage NSCLC. Distant metastasis remains the most common pattern of failure. Longer follow up is needed.

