4.0 Pre-treatment evaluation

- 4.1 Complete History and Physical: A complete history and physical to include performance status, recent weight loss, and concurrent non-malignant disease and its therapy will be recorded within 30 days before registered. (Table 1)
- 4.2 Laboratory and Radiographic Tests
 - 4.2.1 Laboratory studies will include a CBC with differential, platelet count, electrolytes, BUN, creatinine within 30 days. LFTs will be optional. 10 ml of additional peripheral blood will be collected optionally at the time of pre-registration blood work up. The blood sample will be frozen using -80 degree centigrade refrigerator for future biomarker studies. In the future, a separate protocol will be developed for the biomarker studies. (Table 1)
 - 4.2.2 Chest X-ray, MRI or CT scans of the brain, CT of chest or PET scan should be done within 3 months prior to radiotherapy. PET/CT scan is preferred whenever possible. Radionuclide bone scan is optional.
 - 4.2.3 PFTs including FEV1, DLCO, TVC, FEV should be obtained within 3 months prior to radiotherapy. EKG is required within 3 months as a baseline test. Cardiac SPECT is recommended if lesion is close to heart and cardiac toxicity

is of concern and/or when EKG is abnormal.

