8.0 Chemotherapy

Adjuvant Chemotherapy 4 weeks after RT would be allowed at the discretion of the treating physicians.

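### The grade 4–5 safety review requires direct causation by protons, so a severe event only possibly related to protons need not prompt it

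*Combined protocol and SAP*

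**What the plan says.** Section 9.0 contains two safety rules that act on the trial as a whole.

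- **Pneumonitis rule.** "We will monitor the rate of grade 3+ pneumonitis, which is assessed within 3 months following completion of therapy". The prior is given as "We assume a beta(0.2, 1.8) prior distribution for this toxicity rate", and the criterion is that if "there is more than a 92.5% chance that the grade 3+ pneumonitis rate is more than 10% we will stop the trial". The resulting boundaries, as events over patients evaluated, are "4/15, 5/17, 6/24, 7/31, 8/38". The rule says nothing about cause.
- **Grade 4–5 rule.** Added to the first, at the end of the section: "if there is any grade 4 or 5 toxicity directly caused by proton therapy, the trial will be re-evaluated", followed by a decision on changing treatment or stopping. One event is enough, but it must meet the causal condition. The text gives no relatedness scale, no assessor, no time window, and no instruction for an event with a competing cause.

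Section 8.0 states: "Adjuvant Chemotherapy 4 weeks after RT would be allowed at the discretion of the treating physicians". Section 3.1 enrolls inoperable patients with KPS from 60 upward. T1 tumors must lie within 2 cm of structures such as the bronchial tree, great vessels, esophagus or heart. Section 4.2.3 itself anticipates cardiac concern: "Cardiac SPECT is recommended if lesion is close to heart and cardiac toxicity" is an issue.

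**The concern.** Outside early pneumonitis, the whole trial-level safety response rests on one sentence, and that sentence sets a demanding causal test. Two examples show the difficulty. One is a fatal pneumonitis five months after radiotherapy in a patient who has since had chemotherapy. The other is a fatal cardiac event in a patient with heart disease and a tumor beside the heart. In a single-arm trial no comparison group helps to separate the causes. An assessor could reasonably call either event possibly related without calling it directly caused, and on the wording no review would then be required. The pneumonitis rule would catch neither: the first falls after its 3-month window and the second is not pneumonitis.

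These are events the trial has reason to watch. Section 2.0 describes the planned dose as equivalent, for tumor effect, to a photon schedule judged too toxic in the dose-escalation study it cites. It reports a grade 5 esophagitis in that experience and says late toxicity there was the more marked. The protocol expects protons to do better, and the review exists to show if they do not.

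**Working it through.** **1. Does the pneumonitis rule work as stated?** Inputs from Section 9.0: prior beta(0.2, 1.8), stop if P(rate > 10% | data) > 0.925, maximum 40 patients. After x events in n patients the posterior is beta(0.2 + x, 1.8 + n − x).

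- At 4/15 the posterior probability is 0.947, and at 4/16 it is 0.935. From n = 17 a fifth event is needed (5/17 gives 0.979).
- Continuing, the criterion needs 5 events for n = 17–23, 6 for 24–30, 7 for 31–37 and 8 for 38–40. This matches the listed boundaries.
- The probability of stopping early comes from exact binomial recursion, checking after each patient from 15 to 40:

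| True rate | Stated | Recomputed |
|---|---|---|
| 5% | 0.012 | 0.011 |
| 7.5% | 0.053 | 0.050 |
| 10% | 0.131 | 0.135 |
| 15% | 0.413 | 0.422 |
| 20% | 0.709 | 0.717 |
| 25% | 0.895 | 0.898 |
| 30% | 0.970 | 0.972 |

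All agree within 0.01. The posterior criterion alone could be met before patient 15, but the list starts at 15 and the stated operating characteristics match that start. The rule is sound for its purpose. As listed, it cannot act before 15 patients are evaluated or on fewer than 4 events.

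**2. Which severe events does each rule reach?**

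| Event | Pneumonitis rule | Grade 4–5 rule |
|---|---|---|
| Grade 4–5 pneumonitis within 3 months | Counts, whatever the cause | Only if directly caused by protons |
| Grade 4–5 lung event after 3 months | Does not count | Only if directly caused by protons |
| Grade 4–5 esophageal, cardiac, vascular or bronchial event | Does not count | Only if directly caused by protons |

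The Section 5.0 criteria for going off proton treatment include certain grade 4 non-hematological toxicity with no causal condition. They end one patient's treatment and do not call for a trial review.

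**3. How much could the causal condition matter?** Let q be the true proportion of patients with a grade 4–5 toxicity, all taken to be at least possibly related to protons. Let a be the share of those called directly caused. With independent patients,

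P(at least one review in N patients) = 1 − (1 − q·a)^N.

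The documents give neither q nor a, so both are assumptions. For N = 40:

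| q | a = 1 | a = 0.5 | a = 0.25 |
|---|---|---|---|
| 2.5% | 64% | 40% | 22% |
| 5% | 87% | 64% | 40% |
| 10% | 98% | 87% | 64% |

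For q = 5%:
- a = 1: 1 − 0.95^40 = 0.871
- a = 0.5: 1 − 0.975^40 = 0.637
- a = 0.25: 1 − 0.9875^40 = 0.395

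The expected number of patients to the first review is 1/(q·a): 20, 40 and 80, the last being beyond the maximum sample. In the first 20 patients, about one year of planned accrual, the chances are 64%, 40% and 22%.

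**The case against.** The best case for the plan is that the sentence is a supplement. A quantified rule with no causal condition already covers early pneumonitis, including grades 4 and 5. Adverse events are assessed weekly during treatment (Section 5.1), and grade 3 or higher acute and chronic toxicities are to be analyzed with no causal filter (Section 5.2). Severe events will therefore be visible. An investigator may well judge a death on chemotherapy, or a cardiac death beside the treated volume, to be directly caused by protons. A late review may also come after the last patient has been treated, when it can change little. All of this stands, and it limits the harm. It does not close the gap, because none of these provisions requires a trial-level review of a non-pneumonitis or late event that is only possibly related.

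A reader might infer more than the documents support:

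- **That severe events would never reach review, or that sole causation must be proved.** The text asks for direct causation and mentions neither proof nor exclusivity. Early grade 4–5 pneumonitis also counts toward the stopping rule whatever its cause.
- **That the pilot measures the problem.** Section 2.0 reports that of three deaths among 15 patients, "2 had died of metastatic disease and 1 of preexisting cardiac disease". Scaling 1/15 to 40 patients (about 2.7) would estimate comorbid deaths. Nothing shows that this death was a misattributed toxicity; the same paragraph reports no grade 4 or 5 toxicity. The exact 95% interval for 1/15 runs from about 0.2% to 32%. Those patients also had no adjuvant chemotherapy, so neither the death nor the absence of grade 4–5 toxicity informs the chemotherapy setting.
- **That each unattributed event lowers sensitivity proportionately.** One attributed event suffices. At q = 10%, halving a lowers the chance of review from 98% to 87%.
- **That heavy comorbidity is documented.** Inoperability and the KPS range suggest it, but its burden is not quantified, and no chemotherapy uptake is given.

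**Conclusion.** The point holds as a weakness in the trigger's wording. For grade 4–5 events other than pneumonitis within 3 months, the only trial-level trigger in the text depends on a finding of direct causation. The design makes that finding difficult, and a possibly related event need not prompt review.

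The size is illustrative. At an assumed 5% grade 4–5 rate, the chance of any review in 40 patients falls from 87% to 64% or 40% as the share called directly caused falls from all to a half or a quarter. This rests on assumed q and a, on independence between patients, and on every event in q being at least possibly related. The documents do not show that under-attribution would occur or how often. Part of the document was not available for this review, so a monitoring process described there cannot be ruled out. The change is worth making because it is cheap and bears on patient safety.

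**What to change.** In the last sentence of Section 9.0:

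1. Replace the direct-causation condition with *at least possibly related to* proton therapy.
2. Keep the present scope of any grade 4 or 5 toxicity. Limiting it to non-hematological events would narrow the trigger.
3. Add that concurrent or prior chemotherapy, or pre-existing disease, does not by itself exclude an event.
4. Record relatedness for each grade 4–5 event together with the dates of any chemotherapy.

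The consequence, re-evaluation followed by a decision, stays as written. The point does not call for a trigger on all non-cancer deaths, which would turn a toxicity rule into a mortality rule. The cost is a revised sentence, one recorded item with dates, and a few additional safety reviews, some of which will find no relationship to protons. No patients or study procedures are added.
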